#### **12.7.3.3. MR Scan Sequences Protocol**

Refer to Table 29-1 in Section 29 for the MR Scan Sequences Protocol.

The following data is required to be collected:

1. Medications used for sedation in the MR scanner, if applicable
2. MR Scanner manufacturer and model
3. Time of MR scan initiation
4. Time duration for each sequence within the RF intensive and Gradient intensive scans
5. Total duration of RF intensive scan sequences
6. Total duration of Gradient intensive scan sequences
7. Time of MR scan completion

#### **12.7.3.4. Exiting the MRI Protection Mode**

Upon completion of the MR scan, program the PG out of the MRI Protection Mode. It is recommended to program the PG out of MRI Protection Mode as close to the end of MR scan as possible.

- Document the Time of exiting MRI Protection Mode.

Note: The PRM is MR Unsafe and must remain outside the MRI site Zone III (and higher).

Under no circumstances should the PRM be brought into the MRI scanner room, the control room, or the MRI site Zone III or IV areas.

Upon exiting the MRI Protection Mode, all parameters are restored to pre-MRI Protection Mode values with two exceptions:

- Restoration of function of the Minute Ventilation (MV) sensor is delayed. If MV was programmed to ON or Passive at the time of entry into MRI Protection Mode, upon exit from the mode, an automatic six hour calibration of the sensor will begin. MV-driven rate response is not available during this calibration period. If MV-driven rate response is desired sooner, a manual calibration can be performed.

- The Beeper will remain OFF upon exiting MRI Protection Mode.

#### **12.7.4. Device Evaluation after the MR Scan**

1. All implanted leads will be evaluated within two hours upon exit from the MRI Protection Mode through the implanted PG **for THREE separate consecutive sets of measurements** using the test parameters listed in Table 12-3:
  - Manual pacing threshold tests, as defined in sections 12.5.1.1, 12.5.1.2 and 12.5.1.3.
  - Sensing amplitude
  - Impedance
  - Shock impedance (RV lead only)
2. Test for phrenic nerve stimulation (PNS) and measure the PNS threshold if detected in the programmed LV lead configuration.
3. Perform an evaluation of Beeper function as defined in section 12.7.1.1.  
Record the measurements in the EDC system.

#### **12.7.5. Completing the MRI Visit**

1. The PG data must be reviewed to document whether any episodes of polymorphic or monomorphic VT or VF that required ATP or shock therapy are present, following the MR scan.
  - a. If polymorphic or monomorphic VT or VF episodes are present:
    - i. Print the 'Arrhythmia Logbook' and 'Selected Episodes Report' (counters and EGMs) using the PRM
    - ii. A copy of the Selected Episode Report(s) with counters and EGMs is expected to be submitted to Boston Scientific within 5 business days using the upload tool in the EDC system
2. Program the device according to physician discretion, and indicate if any permanent device programming was changed
3. Print the 'Quick Notes' Report
4. Perform a Save All:

- a. Save device data to a USB using the programmer “Save All” feature
- b. Label the USB with the subject ID#, Date, and “MRI”
- c. Retain the original USB at the center, and a copy is expected to be submitted to Boston Scientific using the upload tool in the EDC system. Do not make a copy by using the programmer a second time as this will create a new USB with slightly different information.

5. Schedule the MRI+1 Month follow-up visit.
6. Assessment of the quality of the MR image. Radiologist from the investigate site will score the image quality from 1 to 5 based on comparison with site usual scans, with 1 completely unreadable and 5 similar to usual scans.

#### **12.7.6. MRI Visit Source Data Requirements**

Source data requirements at the MRI Visit are described in Table 12-6:

**Table 12-6 MRI Visit Source Documentation Requirements**

Source Documentation Requirement	Disposition
Pre-MR scan: 

• Device Evaluation (pace threshold, sense amplitude, impedance, RV shock impedance, LV Phrenic Stimulation threshold)

• PRM ECG strips from manual threshold tests documenting LOC for all implanted leads

• Evaluation of Beeper function

• Printout of ‘Quick Notes’ Report

• Cardiology and Radiology MRI Conditions of Use are satisfied

• Abnormal rhythms / ectopy (if possible)

• 

	Retain at center
MR scan: 

• MRI Protection Settings Report

• Heart rate in <math>5 \pm 2</math> minute intervals

• Medications used for sedation in the MR scanner, if applicable

• MR Scanner manufacturer and model

• Time of MR scan initiation

	Retain at center

 
• Time duration for each sequence within the RF intensive and Gradient intensive scans
 
• Total duration of RF intensive scan sequences
 
• Total duration of Gradient intensive scan sequences
 
• Time of MR scan completion
 
	
When PG is programmed out of MRI Protection Mode: 
 
• Time of exiting MRI Protection Mode
 
	Retain at center
Post-MR scan: 
 
• Device Evaluation (pace threshold, sense amplitude, impedance, RV shock impedance, LV Phrenic Stimulation threshold)
 
• PRM ECG strips from manual threshold tests documenting LOC for all implanted leads
 
• Evaluation of Beeper function
 
• Document if polymorphic or monomorphic VT/VF episodes requiring therapy, are present
 
• Documentation of spontaneous VT/VF episode(s) by PRM strips, as applicable: 
 
■ ‘Selected Episodes Report’ (counters and EGMs required)
 
■ ‘Arrhythmia Logbook’
 
 
 
• Printout of ‘Quick Notes’ Report
 
• Assessment of MR scan image quality
 
	Retain at center
Adverse Events	Retain at center
MR scanner DICOM dump/ report file including items such as scan sequence settings and durations as well as calculated scan metrics such as whole body average SAR. The DICOM file must contain both images and scan sequence data.	Retain the original at the center and submit a copy to Boston Scientific
Save All	Retain the original at the center and submit a copy to Boston Scientific

## **12.8. MRI + 1 Month Visit**

The MRI + 1 Month Visit must be performed as a clinic visit and will occur at  $30 \pm 7$  days after the MRI Visit.

### **12.8.1. Device Evaluation**

1. All implanted leads will be evaluated through the implanted PG **for THREE separate consecutive sets of measurements** using the test parameters listed in Table 12-3:
  - Manual pacing threshold tests, as defined in sections 12.5.1.1, 12.5.1.2 and 12.5.1.3.
  - Sensing amplitude
  - Impedance
  - Shock impedance (RV lead only)
2. Test for phrenic nerve stimulation (PNS) and measure the PNS threshold if detected in the programmed LV lead configuration
3. Record the measurements in the EDC system.

### **12.8.2. Completing the MRI + 1 Month Visit**

1. The PG data must be reviewed to document whether any episodes of polymorphic or monomorphic VT or VF that required ATP or shock therapy are present, following the MR Visit.
  - a. If polymorphic or monomorphic VT or VF episodes are present:
    - i. Print the ‘Arrhythmia Logbook’ and ‘Selected Episodes Report’ (counters and EGMs) using the PRM
    - ii. A copy of the Selected Episode Report(s) with counters and EGMs is expected to be submitted to Boston Scientific within 5 business days using the upload tool in the EDC system
2. Program the device according to physician discretion, and indicate if any permanent device programming was changed
3. Print the ‘Quick Notes’ Report
4. Perform a Save All:

- a. Save device data to a USB using the programmer “Save All” feature
- b. Label the USB with the subject ID#, Date, and “MRI + 1 Month”
- c. Retain the original USB at the center, and a copy is expected to be submitted to Boston Scientific using the upload tool in the EDC system. Do not make a copy by using the programmer a second time as this will create a new USB with slightly different information.

5. Schedule the MRI+1 Year follow-up visit.

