### **8.3. Ancillary Assessments**

1. Assessment of RV and LV impedances
2. Assessment of RA lead measurements
3. Assessment of VT/VF episodes post-MR-scan
4. Assessment of programming the MRI Protection Mode
5. Assessment of Image Artifacts for non-medically necessary MR scans.

The MR ICD study referenced FDA IDE trial ENABLE MRI. The major difference is that ENABLE MRI will collect 25 episodes of VT/VF events post MR scan, while the small sample size MR ICD study would use shocking impedance measurement to evaluate the

integrity of the shocking circuit. The MR ICD study will also assess any VT/VF event post MR scan.

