### **12.9.1. Device Evaluation**

1. The standard of care evaluation for device performance is recommended. Record the available measurements in the EDC system.
  - Pacing thresholds
  - Sensing amplitude
  - Impedance
  - Shock impedance (RV lead only)
2. If any new episodes of polymorphic or monomorphic VT or VF that required ATP or shock therapy are present since the prior study visit:
  - i. Print the 'Arrhythmia Logbook' and 'Selected Episodes Report' (counters and EGMs)
  - ii. A copy of the Selected Episode Report(s) with counters and EGMs is expected to be submitted to Boston Scientific within 5 business days using the upload tool in the EDC system
3. Program the device according to physician discretion, if applicable
4. Print the 'Quick Notes' Report

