#### **13.2.3. Assessment of VT/VF post MR scan**

The detection time (first elapsed time), therapy given and conversion result, shocking impedance (if applicable) for post MR scan VT/VF episodes will be presented in the study report.

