### **3.3 Ancillary Assessments**

*The ancillary endpoints are not formal endpoints*

- Changes in RV and LV impedances pre-MR scan versus 1 Month post-MR scan (MRI Visit and MRI + 1 Month Visit) assessed for RV and LV Impedances
- Changes in RA lead measurements including pacing thresholds, sensed amplitudes and impedances, between pre- and 1 Month post-MR scan measurements assessed for RA lead measurements
- The detection time (first elapsed time), therapy given and conversion result, shocking impedance (if applicable) assessed for post MR scan VT/VF episodes. For a VT/VF episode, there might be no therapy, ATP or Shock therapy. Only shock therapy will have a shocking impedance, while shock for VT/VF might be very few in this small sample study. Data collected from Arrhythmia Logbook Report used for Assessment of VT/VF post MR scan and only VT/VF episodes from Arrhythmia log book considered for analysis. Detection time, Therapy given are summarized based on subject total episodes from visit and shocking impedance summarized based on subjects.
- The following information will be summarized for both study-related MR scans and medically necessary MR scans:
  - Duration of the PG in the MRI Protection Mode
  - Time from the start of the MRI Protection Mode to the start of the MR scan
  - Time from the end of the MR scan to exiting the MRI Protection Mode
- MR image quality scores will be presented in study report for assessment of Image Artifacts for non-medically necessary MR scans

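### The Arrhythmia Logbook that feeds the post-scan VT/VF summary is printed under triggers tied to therapy, although the plan promises to assess every VT/VF event and expects some untreated ones

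*Combined protocol and SAP*

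**What the plan says.** **What is promised.** Protocol 8.3, repeated in 9.2, explains that the parent study collects 25 VT/VF episodes after the scan, whereas this small study relies on shocking impedance. It then adds: "The MR ICD study will also assess any VT/VF event post MR scan". Protocol 13.2.3 describes the output as detection time, "therapy given and conversion result, shocking impedance (if applicable) for post MR scan VT/VF episodes will be presented". Neither place sets a therapy condition.

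**What the SAP expects.** SAP 3.3 says: "For a VT/VF episode, there might be no therapy, ATP or Shock therapy". It takes the VT/VF data from the Arrhythmia Logbook Report and from nothing else. SAP 5.1.3 adds a listing from the same Logbook.

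**What sites are told to do.** At the MRI Visit (12.7.5) the device data are reviewed for "any episodes of polymorphic or monomorphic VT or VF that required ATP or shock therapy are present, following the MR scan". The MRI + 1 Month Visit (12.8.2) has the same sentence: "any episodes of polymorphic or monomorphic VT or VF that required ATP or shock therapy are present". The sub-step beneath it, which calls for the Logbook and the Selected Episodes Report, begins "If polymorphic or monomorphic VT or VF episodes are present" and has no therapy condition. At the three-month visits (12.9.1) the trigger for printing is itself limited: "If any new episodes of polymorphic or monomorphic VT or VF that required ATP or shock therapy are present since the prior study visit". The 1-year visit (12.10) and the additional visits (12.11.2) use the same trigger.

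**The concern.** The summary is meant to show whether the system still detects and treats VT/VF after a scan. Its rows include the therapy given, and one admissible value is none. If the document that supplies the data is printed only when therapy was required, episodes are selected partly on the variable being reported. Untreated episodes would be under-represented, the therapy-given results would lean towards treated ones, and detection times would come mainly from episodes that reached therapy.

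This is the only planned summary of detection, therapy and conversion after the scan. Shocking impedance speaks to the integrity of the shocking circuit, and no visit section calls for induced-arrhythmia testing. SAP 3.3 also expects very few shocks, so one missing episode could visibly change the table.

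**Working it through.** The plan has no figure to reproduce here. The check sets the instructions for each post-scan visit side by side.

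| Visit (protocol section) | Review or trigger sentence | Logbook print step | VT/VF line in source table | Save All |
|---|---|---|---|---|
| MRI (12.7.5) | Limited to therapy | Sub-step a, no limit stated | Table 12-6: one limited line, one unlimited | Instructed |
| MRI + 1 Month (12.8.2) | Limited to therapy | Sub-step a, no limit stated | Table 12-7: unlimited | Instructed |
| Three-month (12.9.1) | Limited to therapy | Governed by the limited sentence | Table 12-8: unlimited | Not listed |
| Implant + 1 Year (12.10) | Limited to therapy | Governed by the limited sentence | Table 12-9: unlimited | Instructed |
| Additional (12.11.2, recommended) | Limited to therapy | Governed by the limited sentence | Table 12-10: unlimited, recommended | Recommended |

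Table 12-11, for medically necessary scans, repeats the pair of lines in Table 12-6, both as recommended items.

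1. **Count.** All 5 visit types carry the limit in the review or trigger sentence. In 3 of 5 it directly governs printing of the Logbook. In the other 2 the print step drops it but sits beneath a limited sentence, so sites can read it either way.

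2. **Follow-up time under the explicit limit.** Inputs from Table 12-1 are the scan at 6-9 weeks (day 42-63), the 1-month visit at 30 ± 7 days after it, and the 1-year visit at 365 ± 45 days from implant. Assume no system revision delays the scan.
   - Nominal post-scan time is 365 − 63 = 302 to 365 − 42 = 323 days. The first 30 days are 30/302 = 9.9% to 30/323 = 9.3% of it, so about 90% falls after the 1-month visit.
   - At the window extremes, the first period is 37/(320 − 63) = 37/257 = 14.4% or 23/(410 − 42) = 23/368 = 6.3%, leaving 86% to 94%.
   - This is a share of time, not of episodes.

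3. **Effect on the summary.** Let T be treated episodes, U1 untreated episodes that appear on a printed Logbook, and U2 untreated episodes for which none is printed. Assume a printed Logbook shows all stored episodes.
   - No-therapy share over all stored episodes: (U1 + U2)/(T + U1 + U2).
   - Share the plan would report: U1/(T + U1).
   - If U2 = 0 the two agree. If every untreated episode falls in U2, then U1 = 0 and the reported no-therapy share is 0, whatever the true share.
   - The documents give no value for T, U1 or U2, so only these limits can be stated.

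**The case against.** Several stronger readings are tempting, and the documents do not support them.

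- **That only treated episodes are collected.** At the two visits nearest the scan the print step carries no therapy limit. Tables 12-6 to 12-9 each ask for spontaneous VT/VF episodes, naming the Logbook, without that limit. A Save All copy goes to the sponsor at the MRI, 1-month and 1-year visits. The documents do not say whether these files hold the episode log, and the SAP does not use them for VT/VF. Irretrievable loss is therefore not shown.
- **That failures to treat are excluded.** The wording is required, not received. An episode that needed therapy and got none can be read as inside the instruction. This objection stands, but it leaves the wording ambiguous, and it does not help with episodes judged not to need therapy, which SAP 3.3 still expects to tabulate.
- **That untreated episodes are the most telling sign of lost function.** Nothing in the documents says so. An untreated episode may be benign.

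The stakes are also limited. Protocol 13.2 and SAP 3.3 state that ancillary assessments are not formal endpoints, and no success criterion attaches to VT/VF. Permanent loss of defibrillation counts in the primary safety endpoint when it is related to the scan and system. Shocking impedance and RV sensed amplitude are primary effectiveness endpoints. Serious adverse events and device deficiencies are reportable through the end of the study.

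What remains is a mismatch in scope between promise, trigger, source tables and SAP, and two readings open to sites.

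**Conclusion.** The concern holds as an inconsistency in data collection for an ancillary summary. It is firmest at the three-month, 1-year and additional visits, where the trigger is explicitly limited and, for the first two, contradicts Tables 12-8 and 12-9. At the MRI and 1-month visits the text is mixed, and the risk is uneven site practice. A subject with only untreated stored episodes may have no Logbook and so be absent from the VT/VF summary and listing.

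The direction of any distortion is towards treated episodes. Its size cannot be derived: it depends on how many stored episodes go untreated, whether the same subject also had a qualifying episode, and which instruction a site follows. No primary safety or effectiveness endpoint changes. The change is worth making because it is cheap and concerns the only planned account of detection, therapy and conversion after the scan.

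**What to change.** Use one definition of a collectable episode: a VT/VF episode stored by the pulse generator after the scan, whether or not therapy was delivered. Put it in place of the therapy-limited wording in 12.7.5, 12.8.2, 12.9.1, 12.10 and 12.11.2, and in the lines of Tables 12-6 and 12-11 that refer to episodes requiring therapy. Ask for the Logbook to be printed for each such episode.

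In SAP 3.3, make all such episodes the denominator and tabulate no therapy, ATP and shock separately. If the Save All files hold the episode log, the SAP could name them as a second source.

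The cost is a wording change and a few more printouts and uploads, as the device is already interrogated at these visits. Device programming and treatment are untouched. One gap remains: episodes the device never detected or stored would still be missed, and the report should say so.

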#### **12.8.3. MRI + 1 Month Visit Source Data Requirements**

Source data requirements at MRI+1 month Visit are described in Table 12-7:

**Table 12-7 MRI + 1 Month Source Documentation Requirements**

Source Documentation Requirement	Disposition
Device Evaluation (pace threshold, sense amplitude, impedance, RV shock impedance, LV Phrenic Stimulation threshold)	
PRM ECG strips from manual threshold tests documenting LOC for all implanted leads	
Printout of ‘Quick Notes’ Report	
Documentation of spontaneous VT/VF episode(s) by PRM strips, as applicable: 

• ‘Selected Episodes Report’ (counters and EGMs required)

• ‘Arrhythmia Logbook’

	Retain at center
Adverse Events	
Save All	Retain the original at the center and submit a copy to Boston Scientific

#### **12.9. Every Three-month Follow ups through Three Years (Recommended)**

An in-clinic follow-up schedule of every three months is strongly recommended to monitor device performance. The first Every 3-month visit will occur  $90 \pm 14$  days after MRI visit. Subsequent Every 3-month follow-up visits will be scheduled every three months ( $90$  days  $\pm 14$  Days) from the previous scheduled study follow-up.

### **12.9.1. Device Evaluation**

1. The standard of care evaluation for device performance is recommended. Record the available measurements in the EDC system.
  - Pacing thresholds
  - Sensing amplitude
  - Impedance
  - Shock impedance (RV lead only)
2. If any new episodes of polymorphic or monomorphic VT or VF that required ATP or shock therapy are present since the prior study visit:
  - i. Print the 'Arrhythmia Logbook' and 'Selected Episodes Report' (counters and EGMs)
  - ii. A copy of the Selected Episode Report(s) with counters and EGMs is expected to be submitted to Boston Scientific within 5 business days using the upload tool in the EDC system
3. Program the device according to physician discretion, if applicable
4. Print the 'Quick Notes' Report

### **12.9.2. Every Three-month Visit Source Data Requirements**

Source data requirements at Every Three-month visits are described in Table 12-8.

**Table 12-8 Every Three Month Source Documentation Requirements**

Source Documentation Requirement	Disposition
Documentation of spontaneous VT/VF episode(s) by PRM strips, as applicable: 

• 'Selected Episodes Report' (counters and EGMs required)

• 'Arrhythmia Logbook'

	Retain at center
Printout of 'Quick Notes' Report	
Adverse Events	

### **12.10. Implant + 1 Year Visit**

The Implant + 1 Year Visit must be performed as a clinic visit and will occur at  $365 \pm 45$  days

after implant.

#### Device Evaluation

1. The standard of care evaluation for device performance is recommended. Record the available measurements in the EDC system.
  - Pacing thresholds
  - Sensing amplitude
  - Impedance
  - Shock impedance (RV lead only)
2. If any new episodes of polymorphic or monomorphic VT or VF that required ATP or shock therapy are present since the prior study visit:
  - i. Print the ‘Arrhythmia Logbook’ and ‘Selected Episodes Report’ (counters and EGMs)
  - ii. A copy of the Selected Episode Report(s) with counters and EGMs is expected to be submitted to Boston Scientific within 5 business days using the upload tool in the EDC system
3. Program the device according to physician discretion, if applicable
4. Print the ‘Quick Notes’ Report
5. Perform a Save All:
  - a) Save device data to a USB using the programmer “Save All” feature
  - b) Label the USB with the subject ID#, Date, and “MRI + 1 Year”
  - c) Retain the original USB at the center, and a copy is expected to be submitted to Boston Scientific using the upload tool in the EDC system. Do not make a copy by using the programmer a second time as this will create a new USB with slightly different information.

#### **12.10.1.Implant + 1 Year Visit Source Data Requirements**

Source data requirements for Implant +1 Year Visit are described in Table 12-9.

**Table 12-9 Implant + 1 Year Source Documentation Requirements**

Source Documentation Requirement	Disposition
Device Evaluation (pace threshold, sense amplitude,	Retain at center

impedance, RV shock impedance)	
PRM ECG strips from manual threshold tests documenting LOC for all implanted leads	
Documentation of spontaneous VT/VF episode(s) by PRM strips, as applicable: 

• ‘Selected Episodes Report’ (counters and EGMs required)

• ‘Arrhythmia Logbook’

	
Printout of ‘Quick Notes’ Report	
Adverse Events	
Save All	Retain the original at the center and submit a copy to Boston Scientific

